3.10 Interventional safety assessment

3.10.1 Adverse Events (AEs) / Serious Adverse Events (SAEs): Definitions

For this study, the study investigators define adverse events as “an abnormal sign, symptom, laboratory test, syndromic combination of such abnormalities, untoward or unplanned occurrence (e.g. an accident), or any unexpected deterioration of concurrent illness”.³⁹ For serious adverse events (SAEs), they are defined according to the USA Code of Federal Regulations Title 21, Section 312.32 which is “adverse events result in the following outcomes: 1) death; 2) life-threatening AEs; 3) inpatient hospitalization or prolongation of existing hospitalization; 4) a persistent or significant incapacity or substantial disruption of the ability to conduct normal life functions, or a congenital anomaly / birth defect”.⁴⁰ Other significant medical events are also considered as SAEs if the events compromise the study participants and result in the requirement of medical or surgical intervention to prevent one of the outcomes above. As an example, allergic bronchospasm requiring intensive treatment in an emergency setting to prevent the outcomes above.

3.10.2: The likelihood of AEs / SAEs: Classification of causality

The likelihood of AEs and SAEs are classified based on the modified Naranjo et al. 1981 recommendations as follows:⁴¹

- a) **Unrelated:** The AEs / SAEs are unlikely related to microneedle or EMLA application.
- b) **Possible:** The connection between AEs / SAEs with microneedle or EMLA cannot be excluded with absolute certainty:

- i) There is a temporal relationship between the microneedle / EMLA application with the occurrence of AEs / SAEs.
- ii) However, there is an alternative factor (e.g. characteristic of patient's disease / clinical state) that can possibly or likely explain such a relationship or a significant uncertainty exists over the cause of AEs / SAEs
- c) **Probable:** The connection between AEs / SAEs with microneedle or EMLA has a high degree of certainty
 - i) There is a temporal relationship between the microneedle / EMLA application with the occurrence of AEs / SAEs
 - ii) AEs / SAEs disappear or decreases upon the withdrawal of microneedle or EMLA application but do not reappear upon subsequent microneedle / EMLA application
 - iii) Alternative causes cannot reasonably explain the relationship between microneedle / EMLA application with the occurrence of AEs / SAEs.
- e) **Definite:** The AEs / SAEs are obviously linked to microneedle / EMLA application with the occurrence of AEs / SAEs
 - i) There is a temporal relationship between the microneedle / EMLA application with the occurrence of AEs / SAEs
 - ii) AEs / SAEs disappear or decreases upon the withdrawal of microneedle or EMLA application and reappears on subsequent microneedle or EMLA application.
 - iii) No other alternative causes.

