3.10.3 Methods for assessing and recording of AEs / SAEs

The study protocol will be halted at any moment of the study period if the study participants develop any sudden (expected or unexpected) severe complications / adverse events. The withdrawal of a study participant from the trial will be documented on the adverse event page of the CRF and the participant will be further followed up for the study outcomes and included in the analysis as per the original randomization group (intention-to-treat analysis). All AEs / SAEs will be recorded and graded according to the Common Terminology Criteria for Adverse Events (CTCAE) version 5 and US FDA's Toxicity Grading Scale Healthy Adults and Adolescents Volunteers Enrolled in Preventive Vaccine Clinical Trials criteria as shown in Appendix III and IV.^{42,43}

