3.10.7 Study Halting Criteria

Participant enrolment and allocation and institution of interventions will be stopped if one of the following occur:

- a) Death related to microneedle or EMLA application
- b) Any participant experiences bronchospasm, laryngospasm or anaphylaxis within 24 hours post microneedle or EMLA application
- c) Any SAE related to microneedle or EMLA application
- d) Any AE of grade 3 and above or any SAE that cannot obviously be implicated on other causes
- e) Any study participant who develops abscess / ulceration / erosion at the site(s) of microneedle or EMLA application

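### Section 3.10.2: the conditions for Probable and Definite cannot be met by a death or other irreversible event, and Probable does not say how to grade a resolving event after which nothing was re-applied

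*Combined protocol and SAP*

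**What the plan says.** Section 3.10.2 has four categories, each with a lead definition. All but Unrelated add numbered conditions, and condition i is always a temporal relationship.

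- **Unrelated:** a link is unlikely.
- **Possible:** condition ii asks for an alternative factor "that can possibly or likely explain such a relationship or a significant uncertainty exists over the cause of AEs / SAEs".
- **Probable:** condition ii is "AEs / SAEs disappear or decreases upon the withdrawal of microneedle or EMLA application but do not reappear upon subsequent microneedle / EMLA application". Condition iii is that no alternative cause is a reasonable explanation.
- **Definite:** condition ii is "AEs / SAEs disappear or decreases upon the withdrawal of microneedle or EMLA application and reappears on subsequent microneedle or EMLA application". Condition iii is that there is no alternative cause.

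Two other sections decide whether a later application takes place. Section 3.10.3 states: "The study protocol will be halted at any moment of the study period if the study participants develop any sudden (expected or unexpected) severe complications". Section 3.10.7 states: "Participant enrolment and allocation and institution of interventions will be stopped if one of the following occur". Its triggers include (b), "Any participant experiences bronchospasm, laryngospasm or anaphylaxis within 24 hours post microneedle or EMLA application", and (d), "Any AE of grade 3 and above or any SAE that cannot obviously be implicated on other causes".

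Section 3.10.1 counts death among the SAE outcomes. Section 3.10.4 has the possible causal link recorded for each local skin reaction, and 3.10.5 applies a similar procedure to systemic reactions.

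**The concern.** Condition ii of Probable presupposes two observations: that the event lessened after withdrawal, and what happened at the next application. For the worst events one or both may be unobtainable. A death cannot lessen. A child or a trial that has been stopped has no further study application, and the protocol is right to ensure that. The causality scale therefore leans on a re-application that the protocol's own safety rules prevent.

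At stake is the accuracy of the safety record in a phase II trial of a microneedle prototype in children. An irreversible event with no other explanation would be recorded too low or could not be placed. Two assessors could also grade the same resolved event differently, depending on how they read the clause on reappearance.

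**Working it through.** The plan gives no figure to reproduce. The check is to run the possible sets of facts through the definitions.

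**Inputs.** The conditions are those of 3.10.2, applied together within each category. Timing fits in every row. An event judged unlikely to be related would be Unrelated and is left out.

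**Two readings of the reappearance clause in Probable ii.** On the strict reading a later application must have taken place. On the lenient reading the clause is also met when nothing was re-applied.

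| Alternative factor | Significant uncertainty | Lessens on withdrawal | Later application | Strict | Lenient |
|---|---|---|---|---|---|
| no | no | yes | event reappears | Definite | Definite |
| no | no | yes | event does not reappear | Probable | Probable |
| no | no | yes | none given | no match | Probable |
| no | no | no | any | no match | no match |
| no | yes | yes | none given | Possible | Possible or Probable |
| no | yes | no | any | Possible | Possible |
| yes | either | either | any | Possible | Possible |

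**Irreversible events.** These are the rows with no lessening. Neither reading gives Probable or Definite. The grade is Possible if there is an alternative factor or significant uncertainty. Otherwise nothing matches.

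**Resolving events with no later application.** With no alternative factor and no significant uncertainty, the result turns wholly on the reading: no match on the strict one, Probable on the lenient one.

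**When a later application is absent by design.**
- After a trigger in 3.10.7, interventions stop for everyone. On its natural reading, 3.10.3 stops the affected child after a sudden severe event.
- At the last visit no study application follows. This is one of the four planned applications per child.
- For the microneedle alone, 26 children (3.12) each receive three microneedle arms (3.15, Table 1), so 26 × 3 = 78 applications are planned. Each child has exactly one last microneedle application, so 26/78 = 33% have no later one in the study. This is a share of applications, not of events.

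**Where the grade is used.**
- *Halting:* 3.10.7(d) acts on any AE of grade 3 or above, or any SAE, unless another cause is obvious. It needs no causality grade. Items (a) and (c) refer to relatedness, but (d) covers an unexplained death or SAE in any case.
- *Reporting:* 3.10.6 sends all SAEs to the ethics committee within 24 hours whatever their grade, and provides for a follow-up report.
- *Analysis:* nothing in 3.14 uses the grade.

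**The case against.** The strongest reply is that the strict reading is a choice. Section 3.10.2 does not say that every numbered condition must hold, or that the reappearance clause needs an actual re-application. A clinician could take it as meaning that the event has not come back, and could be guided by the lead definitions, which speak of degrees of certainty. This largely stands for events that resolve. A reader might infer that a first severe event which stops treatment fits no category at all. The documents support that on one reading only.

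Nor is a first anaphylaxis under EMLA a clean example. The adhesive dressing (3.9.2) and the PainMonitor electrodes (3.9.3) are on the child at the same time, and 3.6 itself treats plaster and electrodes as allergy risks. An assessor could point to an alternative factor or real uncertainty, and Possible would then be available.

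A reader might also extend the point to every SAE outcome that sounds lasting. Section 3.10.1 includes "a persistent or significant incapacity or substantial disruption of the ability to conduct normal life functions", and such an outcome can lessen over time. Only death and truly irreversible events are excluded by the lessening condition.

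For last-visit events, condition ii is not limited to study applications. EMLA is usual practice at this day-care centre (3.9.2), and these children are transfused regularly (3.4), so later EMLA exposure after a mild event is likely. Later microneedle exposure outside the trial is not described.

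What the reply does not reach is the irreversible event with no other cause. The lenient reading does not help it. Citing significant uncertainty to place it under Possible would record a doubt that the facts do not raise.

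**Conclusion.** Wrong as written, and minor. While conditions i to iii apply together, a death or other irreversible event with no alternative cause cannot be graded Probable or Definite. A resolving event with no later application is Probable only on a reading that the text does not state.

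The effect is confined to the recorded causality grade. A reader might infer that a related death could fail to halt the trial, or that the trial's results are at risk. The documents do not support either: 3.10.7(d) stops the trial without a causality grade, 3.10.6 reports every SAE, and 3.14 does not use the grade. How many children would be affected cannot be stated, because the documents give no event rate.

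The conclusion rests on two assumptions. The first is that the numbered conditions are cumulative. The second is that no further category exists: the list runs a, b, c, e, so a category (d) may be missing from the available copy.

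**What to change.** 1. Check the master protocol for a category (d) before amending.
2. Reword condition ii of Probable: *AEs / SAEs disappear or decrease upon withdrawal, where this can be observed; re-application is not required, and this condition does not apply to death or other irreversible events.* The words on observation also suit the microneedle, whose maltose dissolves into the skin within about a minute (3.9.1), so that withdrawal is hard to define.
3. Keep reappearance as a condition of Definite, and accept that a stopped child will normally be graded Probable at most. An event that does reappear would then meet both definitions, so state that the higher grade is recorded.
4. Add a CRF field: *re-applied: yes / no*.

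Do not use this amendment to define relatedness in 3.10.7(a) and (c) as every grade other than Unrelated. Possible includes events that another factor likely explains, so that definition would widen the halting rules.

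The cost is a short amendment and one CRF field. Sample size, halting and reporting do not change.

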3.6 Exclusion Criteria

- i) Patient with a previous history of sensitization or allergy to EMLA Cream
- ii) Patient with a previous history of allergy to materials used in the study i.e., plaster, electrodes, maltose, Polyvinyl Alcohol (PVA), and Polyethylene Terephthalate (PET)
- ii) Patient exposed to analgesic usage within 24 hours prior to the procedure
- iii) Generalized skin disorder/ rash
- iii) Agitated/ fretful patient

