The investigator identified and drew a grid of 1cm × 1cm at the dorsum hand, which served as an ideal site for cannulation. The administrator of intervention (procedurist) will apply either 1 FTU of EMLA Cream (approximately 0.68 g/cm²) or 0.5 FTU (approximately 0.369 g/cm²) over the preparation area. If the patient is subjected to MN patching at his/her visit, the MN patch will be applied by thumb force and pressed firmly against the hand surface for 5 seconds to patch MN to the skin entirely before applying EMLA cream. Otherwise, an empty (i.e. without MN) PVA-containing PET sham patch will be applied instead. Besides, the height-to-base ratio (4:1) used for MN will also optimally minimise its adverse effects (pain, redness), thus preserving the masking (blinding) of study participants from knowing the types of interventions received. The preparation area will be covered with an adhesive dressing (Tegaderm™; 3M, Maplewood, Minnesota, USA) after EMLA cream application. After the allocated application time (15 or 30 minutes), the attending medical officer will set up the transfusion line with a 22-gauge hypodermic needle inserted into the dorsum hand. Throughout the process, the parents/guardians will be allowed to stay by the patient's side at all times.

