3.15 Study flow

[figure not shown]

Figure 4. The flowchart of this randomized crossover trial showing 4 random intervention sequences out of 24 permutations generated. Intervention A: MN + 1 FTU EMLA 30 minutes application; Intervention B: MN + 0.5 FTU EMLA 30 minutes application; Intervention C: MN + 1 FTU EMLA 15 minutes application; Intervention D: 1 FTU EMLA Only 30 minutes (controls)

| | | | |
|------|------|------|------|
| ABCD | BACD | CADB | DABC |
| ACBD | BADC | CABD | DACB |
| ABDC | BDAC | CBAD | DBAC |
| ACDB | BDCA | CBDA | DBCA |
| ADBC | BCAD | CDAB | DCAB |
| ADCB | BCDA | CDBA | DCBA |

Table 1. The exhaustive list of permutations of intervention sequences that will be randomized to the participants of this trial. Intervention A: MN + 1 FTU EMLA 30 minutes application; Intervention B: MN + 0.5 FTU EMLA 30 minutes application; Intervention C: MN + 1 FTU EMLA 15 minutes application; Intervention D: 1 FTU EMLA Only 30 minutes (controls)

[figure not shown]

Figure 5. Schematic flow of the clinical trial.

GANTT CHART

| Project Activities | Timeline of event | | | | | | | | | | | | | | |
|---------------------------------------|-------------------|---|---|---|---|---|---|---|----|----|----|---|------|---|---|
| | 2021 | | | | | | | | | | | | 2022 | | |
| | 2 | 3 | 4 | 5 | 6 | 7 | 8 | 9 | 10 | 11 | 12 | 1 | 2 | 3 | |
| Proposal preparation | ● | ● | ● | ● | ● | | | | | | | | | | |
| Ethics approval | | | | | ● | ● | | | | | | | | | |
| Microneedle fabrication | | | | | ● | ● | ● | | | | | | | | |
| Purchasing of PainMonitor | | | | | ● | ● | ● | | | | | | | | |
| Patients' recruitment | | | | | | ● | ● | ● | | | | | | | |
| Launching of clinical trial | | | | | | ● | ● | ● | ● | ● | ● | ● | ● | ● | ● |
| Data analysis and interpretation | | | | | | | | ● | ● | ● | ● | ● | ● | ● | ● |
| Manuscript preparation and submission | ● | ● | ● | ● | ● | ● | ● | ● | ● | ● | ● | ● | ● | ● | ● |
| End of research project | | | | | | | | | | | | ● | ● | ● | |

BUDGET

| No. | Description | Unit price (RM) | Quantity | Price (RM) |
|-----|---|-----------------|----------|-----------------|
| 1 | RESEARCH MATERIALS & SUPPLIES | | | |
| 1.1 | Schlenker VAS Pain Scale Rulers 0-100mm with Slider | 40 | pcs | 4 160 00 |
| 1.2 | EMLA Cream 5%, 5G, 1s x 5 | 160 | Box | 12 1920 00 |
| 1.3 | Hansaplast Sensitive Kids Plaster 20's | 6 | box | 7 42 00 |
| | | | | |
| 2 | PROFESSIONAL SERVICE | | | |

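### Section 3.10.2 judges causality against microneedle and EMLA as one exposure, so the label cannot name the agent and can read a reaction-free EMLA-only visit as a failed rechallenge

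*Combined protocol and SAP*

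**What the plan says.** Section 3.10.2 has four causality classes: *Unrelated*, *Possible*, *Probable* and *Definite*. Each refers to the microneedle and EMLA jointly, beginning with *Unrelated*: "The AEs / SAEs are unlikely related to microneedle or EMLA application". None asks which of the two is suspected.

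The two upper classes differ chiefly in criterion (ii). For *Probable*, the event lessens or disappears on "withdrawal of microneedle or EMLA application but do not reappear upon subsequent microneedle / EMLA application". For *Definite*, it does so on "withdrawal of microneedle or EMLA application and reappears on subsequent microneedle or EMLA application".

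The arms are defined in section 3.15. A, B and C each combine the microneedle with EMLA. D is EMLA alone, in the same amount and for the same time as A. Section 3.9.2 says of visits without the microneedle: "Otherwise, an empty (i.e. without MN) PVA-containing PET sham patch will be applied instead". There is no microneedle-only arm.

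Other relevant provisions:
- Section 3.8 blinds outcome assessors and care providers to the intervention.
- Section 3.10.4 records, for local reactions, a possible causal link with the study intervention or control, without naming a component.
- Section 3.13 codes the intervention received at each visit.
- Section 3.14 promises descriptive summaries of all data, but plans no tabulation or comparison of adverse events by arm.

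**The concern.** The microneedle is the new component; the cream is what the control visit also receives. A causality label in this trial should therefore be able to say whether the device is implicated, and this one cannot.

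The rechallenge step can also work backwards. In a crossover, D removes the microneedle while EMLA continues. A reaction seen with the microneedle and absent at D is within-child evidence pointing to the microneedle. Because D contains EMLA, the literal wording makes it a subsequent application at which the event failed to reappear, which is the feature of the lower class. The documents do not say how a D visit is to be read, and a blinded assessor cannot settle it at the visit.

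At stake is whether the final report can make a clear statement about device-related reactions, mainly the milder solicited skin reactions, which are the ones that can recur over several visits.

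**Working it through.** **Inputs.** The criteria are those of section 3.10.2, the arms and 24 sequences those of section 3.15 (Table 1), and the 23 required and 26 planned subjects those of section 3.12. The plan gives no figure of its own on this point to reproduce.

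**Step 1: what each visit contains.**

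| Arm | Microneedle | EMLA | Literal pooled reading | Per-component reading |
|---|---|---|---|---|
| A, B, C | yes | yes | re-application | re-application of both |
| D | no (sham) | yes | re-application | microneedle withdrawn, EMLA re-applied |

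**Step 2: how often D follows a microneedle visit.** Table 1 holds 4! = 24 distinct sequences, with D in each of the four positions in 6 of them.
- D comes after at least one microneedle visit unless it is first: 24 − 6 = 18 of 24 (75%).
- There are 24 × 3 = 72 adjacent visit pairs. D is the earlier visit in 18 of them, leaving 72 − 18 = 54 microneedle visits that have a next visit. That next visit is D in 18 of 54 (33%).

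**Step 3: which criteria (ii) are met.** Take a reaction that occurs at every microneedle visit, resolves between visits and is absent at D, in a child who completes all four visits.

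| Position of D | Sequences | Later visit without the reaction (*Probable* ii) | Later visit with it (*Definite* ii) |
|---|---|---|---|
| 1 | 6 | no | yes |
| 2 | 6 | yes (visit 2) | yes (visits 3, 4) |
| 3 | 6 | yes (visit 3) | yes (visits 2, 4) |
| 4 | 6 | yes (visit 4) | yes (visits 2, 3) |

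Both criteria are met in 6 + 6 + 6 = 18 of 24 sequences, and *Definite* (ii) in 24 of 24. A reaction to the cream that recurs at all four visits meets only *Definite* (ii). The microneedle reaction thus acquires a second, conflicting label, depending on where D falls.

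**Step 4: what the A versus D contrast can deliver.** A and D differ only in microneedle versus sham, so the paired difference estimates the effect of adding the microneedle. The documents give no reaction rates. As a range, assume 20%, 30% or 40% in A against 5% in D, with independent responses within a child. The discordant probabilities are b = pA(1 − pD) and c = pD(1 − pA). For 30% versus 5%, b = 0.30 × 0.95 = 0.285 and c = 0.05 × 0.70 = 0.035. Exact two-sided McNemar power at 0.05 is:

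| Assumed A vs D | 23 pairs | 26 pairs |
|---|---|---|
| 20% vs 5% | 14% | 18% |
| 30% vs 5% | 44% | 53% |
| 40% vs 5% | 74% | 81% |

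The 26 includes the 10% attrition allowance, so 23 is the safer basis. The contrast suits an estimate with an interval better than a test.

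**The case against.** The strongest reply is that the wording is disjunctive. D is literally a withdrawal of the microneedle, so the text already permits an agent-by-agent reading, and no section states that D counts as a re-application. That stands in part: the defect is an unresolved ambiguity, not a rule that is wrong on every reading. Nothing in the plan selects the sensible reading, however.

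Four stronger conclusions are tempting, and the documents do not support them.
- **That the cause cannot be told at all.** This is true of the label, not of the trial. The arm is coded per visit, A and D isolate the microneedle's added effect, and section 3.9.3 takes a VAS reading after the patch and before the cream.
- **That microneedle reactions receive lower certainty.** A consistent one meets *Definite* (ii) in all 24 sequences, and taking the highest class met would resolve the overlap. Criterion (iii) on alternative causes applies as well, and cannulation of the same hand is an evident alternative for pain, bruising or swelling.
- **That reactions to other materials must be called *Unrelated*.** Section 3.6 does list "materials used in the study i.e., plaster, electrodes, maltose, Polyvinyl Alcohol (PVA), and Polyethylene Terephthalate (PET" as possible allergens and section 3.10.2 names none of them. *Possible* nevertheless covers a temporal relationship with an uncertain cause, and PVA and PET are part of the patch itself.
- **That the label is the only route to a safety statement.** Reactions are solicited, graded and documented under sections 3.10.3 to 3.10.5, and section 3.14 summarises all data descriptively.

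It is also fair to say that little operational depends on *Probable* versus *Definite*. Ethics reporting (3.10.6) uses grade and seriousness. The halting criteria (3.10.7) turn on named events, relatedness, or the absence of an obvious other cause. Safety is not among the objectives in Chapter II. These points limit the weight of the concern but do not remove it.

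**Conclusion.** The concern holds in a limited form. The causality label in section 3.10.2 cannot identify the agent. On its literal reading it treats a reaction-free D visit as a failure to reappear, when that absence points to the microneedle. A reaction tied consistently to the microneedle then satisfies criterion (ii) of two classes in 18 of 24 sequences. The trial collects the information needed to estimate the microneedle's added effect, but no stated rule or analysis uses it.

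The 18 of 24 assumes a reaction that recurs at each microneedle visit, is absent at D and is seen in a child who completes all four visits. It is a share of the sequences in Table 1, not a forecast of affected children. The point concerns mainly milder reactions, because severe ones may stop the trial before any rechallenge. Sample size, power and alpha for the stated objectives are unaffected. This is a cheap improvement of modest weight.

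**What to change.** In section 3.10.2, classify causality separately for the patch (microneedle or sham) and for EMLA. Define withdrawal and re-application per component, and state that D is a withdrawal of the microneedle and a re-application of EMLA. To keep the blind, the assessor records only the relation to the study application at the visit. The component-level class is derived from the allocation code after unblinding.

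In section 3.14, tabulate each solicited reaction by arm. Report the within-child A versus D difference with an exact 95% CI as the effect of adding the microneedle. The halting wording stays as it is.

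The cost is two CRF fields, revised wording in 3.10.2 and one table. There are three downsides. The component class is known only after unblinding. The interval will be wide for uncommon reactions. And without a microneedle-only arm, direct needle irritation cannot be separated from greater absorption of cream through the microchannels.
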